10.3.1 Predicted Normal HHD Muscle Strength

Muscle Strength

Note: Many of the HHD derived variables detailed below rely on regression equations that have predictor variables in units different than what is found in the analysis datasets. Care will be taken to convert dataset variables to the correct units before they are entered into the prediction equation. The resulting predicted value will then, in turn, be converted to the appropriate unit for analysis.

Hand-Held Dynamometry

Shoulder abduction and hip abduction

Regression Equations and Multiple Correlations of Sex, Age, and Weight with Muscle Strength

Muscle Action	Side	Equation*	R	R ²
Shoulder Abduction	Nondominant	$165.16 - 74.9S - .910A + .126W$.843	.710
	Dominant	$178.90 - 77.1S - 1.128A + .134W$.843	.710
Hip Abduction	Nondominant	$203.32 - 73.3S - 1.247A + .192W$.794	.630
	Dominant	$195.24 - 62.4S - 1.184A + .198W$.764	.584

(Bohannon 1997b)

*Muscle strength results in Newtons (N). S, sex (male=0, female=1); A, age (years); W, weight (Newtons).

Note: Age and weight values collected at the Baseline visit will be used for the calculation of predicted values for shoulder abduction and hip abduction for all study time points.

Hip adduction

Muscle Action	Gender	Side	Age (years)	Equation
Hip Adduction	Female	Left	≤ 55	$19.1 - 0.30*(age - 55)$
		Right	≤ 55	$19.5 - 0.00*(age - 55)$
	Female	Left	> 55	$19.1 - 0.212*(age - 55)$
		Right	> 55	$19.5 - 0.245*(age - 55)$
Hip Adduction	Male	Left	≤ 49	$31.8 + 0.044*(age - 49)$
		Right	≤ 49	$31.6 - 0.082*(age - 49)$
	Male	Left	> 49	$31.8 - 0.280*(age - 49)$
		Right	> 49	$31.6 - 0.206*(age - 49)$

(Stoll et al. 2000)

Median strength results in kiloponds (kp) also known as kilogram-force (kgf)

Note: The age category that applies for a subject at the Baseline visit will be used for the calculation of hip adduction predicted values for all study time points.

Elbow flexion, elbow extension, hip flexion, hip extension, knee flexion, knee extension

Regression Equations for Strength Prediction

Muscle Action	Equation
Right Elbow Flexion	$-(\text{age} * 0.13) + (\text{gender} * 11.24) + ((\text{weight}/\text{height}^2) * 0.07) + 22.78$
Left Elbow Flexion	$-(\text{age} * 0.11) + (\text{gender} * 10.63) + ((\text{weight}/\text{height}^2) * 0.05) + 19.66$
Right Elbow Extension	$-(\text{age} * 0.08) + (\text{gender} * 8.33) + ((\text{weight}/\text{height}^2) * 0.16) + 12.37$
Left Elbow Extension	$-(\text{age} * 0.07) + (\text{gender} * 8.18) + ((\text{weight}/\text{height}^2) * 0.17) + 11.32$
Right Hip Flexion	$-(\text{age} * 0.33) + (\text{gender} * 19.19) + ((\text{weight}/\text{height}^2) * 0.66) + 34.44$
Left Hip Flexion	$-(\text{age} * 0.29) + (\text{gender} * 18.75) + ((\text{weight}/\text{height}^2) * 0.47) + 36.05$
Right Hip Extension	$-(\text{age} * 0.21) + (\text{gender} * 15.19) + ((\text{weight}/\text{height}^2) * 0.14) + 33.52$
Left Hip Extension	$-(\text{age} * 0.23) + (\text{gender} * 15.02) + ((\text{weight}/\text{height}^2) * 0.17) + 33.88$
Right Knee Flexion	$-(\text{age} * 0.16) + (\text{gender} * 8.78) + ((\text{weight}/\text{height}^2) * 0.08) + 22.47$
Left Knee Flexion	$-(\text{age} * 0.17) + (\text{gender} * 7.67) + ((\text{weight}/\text{height}^2) * 0.14) + 21.10$
Right Knee Extension	$-(\text{age} * 0.38) + (\text{gender} * 18.44) + ((\text{weight}/\text{height}^2) * 0.62) + 34.41$
Left Knee Extension	$-(\text{age} * 0.38) + (\text{gender} * 17.68) + ((\text{weight}/\text{height}^2) * 0.62) + 33.61$

(NIMS 1996)

Strength prediction results in kilograms (kg)

Age = years; gender: male = 1, female = 0; weight = kg;; height = meters

Note: Age, height and weight values collected at the Baseline visit will be used for the calculation of predicted values for elbow flexion, elbow extension, hip flexion, hip extension, knee flexion and knee extension for all study time points.

Gross Grip

Normative grip strength values for the Jamar dynamometer for clinical use (in pounds)

Age (years)	Females (n = 355)			Males (n = 365)		
	Number of subjects	5 th %ile Jamar values (lbs)	Median Jamar values (lbs)	Number of subjects	5 th %ile Jamar values (lbs)	Median Jamar values (lbs)
20 - 29	51	50	62	50	81	100
30 – 39	50	49	64	51	80	105
40 – 49	50	48	63	50	78	107
50 – 59	51	45	61	54	73	104
60 – 69	49	40	56	58	64	95
70 - 79	50	32	46	50	51	77
≥ 80	54	22	34	52	34	54

(Peters et al. 2011)

Note: The age category that applies for a subject at the Baseline visit will be used for the calculation of predicted grip values for all study time points.

Walking Ability

Calculation of Predicted Six-Minute Walk Test Distance

6MWT Distance (meters) = 868.8 - (2.99*Age) - (74.7*Gender)

Age in years. Men = 0 and Women = 1.

Note: The age of a subject at the Baseline visit will be used for the calculation of 6MWT predicted values for all study time points.

Table 6: Regression Equations and Multiple Correlations of Sex, Age, and Weight with Muscle Strength (Newtons)

Muscle Action	Side	Equation*	R	R ²
Wrist extension	Non	114.36 - 45.1S - .774A + .094W	.825	.680
	Dom	123.65 - 48.5S - .784A + .092W	.826	.683
Elbow flexion	Non	188.25 - 89.2S - .650A + .132W	.882	.779
	Dom	188.36 - 96.5S - .610A + .140W	.907	.822
Elbow extension	Non	150.37 - 71.5S - 1.044A + .126W	.852	.726
	Dom	156.49 - 73.0S - 1.032A + .116W	.853	.727
Shoulder lateral rotation	Non	140.32 - 50.2S - 50.164A + .080W	.786	.618
	Dom	147.66 - 54.5S - .930A + .088W	.810	.656
Shoulder extension	Non	260.18 - 113.5S - 1.888A + .202W	.842	.709
	Dom	278.99 - 120.0S - 1.99A + .202W	.855	.731
Shoulder abduction	Non	165.16 - 74.9S - .910A + .126W	.843	.710
	Dom	178.90 - 77.1S - 1.128A + .134W	.843	.710
Ankle dorsiflexion	Non	302.54 - 60.9S - 2.203A + .159W	.742	.550
	Dom	285.46 - 47.6S - 2.367A + .193W	.669	.448
Knee extension [†]	Non	480.70 - 95.0S - 4.868A + .310W	.826	.683
	Dom	465.22 - 84.7S - 4.803A + .325W	.820	.673
Hip flexion	Non	216.48 - 74.6S - .926A + .026W	.718	.516
	Dom	219.30 - 72.6S - .977A + .027W	.731	.534
Hip abduction	Non	203.32 - 73.3S - 1.247A + .192W	.794	.630
	Dom	195.24 - 62.4S - 1.184A + .198W	.764	.584

*S, sex (male = 0, female = 1); A, age (years); W, weight (Newtons).

[†]The equations for knee extension are compromised by the upper limit of force (650N) recorded for 21 subjects.

Wrist extension ([Bohannon 1997a](#))

Pinch Strength Norms for Adults

Average Performance of All Subjects on Key Pinch (kg.)

		Men			Women		
Age	Hand	Mean	SD	Range	Mean	SD	Range
20-24	R	11.8	1.6	9.5-15.4	8.0	0.9	6.4-10.4
	L	11.2	1.5	8.6-14.1	7.3	1.0	5.9-10.4
25-29	R	12.1	2.2	8.6-18.6	8.0	1.0	6.4-10.0
	L	11.3	2.0	8.6-17.7	7.5	1.0	5.9-10.0
30-34	R	12.0	2.2	9.1-16.3	8.5	1.4	5.9-11.3
	L	11.9	2.3	7.7-16.3	8.1	1.6	5.4-11.8
35-39	R	11.8	1.5	9.5-14.5	7.5	0.9	5.4-9.5
	L	11.6	1.8	8.2-14.5	7.3	1.2	5.4-10.0
40-44	R	11.6	1.2	9.5-14.1	7.8	1.4	4.5-10.9
	L	11.4	1.8	8.6-14.1	7.2	1.4	3.6-10.0
45-49	R	11.7	1.8	8.6-15.9	8.0	1.5	5.9-10.9
	L	11.2	2.0	8.2-19.1	7.5	1.3	5.4-10.9
50-54	R	12.1	2.0	9.1-15.4	7.6	1.1	5.4-10.0
	L	11.8	1.9	9.1-16.8	7.3	1.2	5.4-10.0
55-59	R	11.0	1.9	8.2-15.4	7.1	1.1	5.0-9.5
	L	10.4	2.1	5.9-14.1	6.7	1.0	5.4-8.6
60-64	R	10.5	2.4	6.4-16.8	7.0	1.2	4.5-9.1
	L	10.1	1.9	7.3-15.0	6.4	1.1	4.5-8.6
65-69	R	10.6	1.8	7.7-14.5	6.8	1.2	4.5-9.5
	L	10.0	1.6	7.7-12.7	6.5	1.3	4.5-9.1
70-74	R	8.8	1.1	7.3-11.3	6.6	1.3	3.6-10.0
	L	8.7	1.4	5.9-12.7	6.3	1.4	4.1-10.0
75 +	R	9.3	2.1	4.1-14.1	5.7	1.0	3.6-7.7
	L	8.7	1.4	5.9-10.9	5.2	1.2	3.2-7.3

The above information is taken from **Grip & Pinch Strength: Normative Data for Adults**, Arch Phys Med Rehabil 66:69-72, 1985, V. Mathiowetz, et al

10.4 Summary of Efficacy Assessment in Parent Studies and in Current Study CL302

Study	Functional Test	Questionnaire	Biomarker
CL-202	Week 0, 12, 36, 60, 84, 108, 132, 156 Muscle strength as measured by HHD; Walking ability as measured by the 6MWT; Arm raising ability as measured by the weighted arm lift test; Functional disability as measured by the GNEM-FAS.	Week 0, 12, 36, 84, 156 None	Week 0, 12, 16, 36, 60, 108, 156 CK Free Serum SA Free and total urine SA (Part I only, Week 0, 12) Serum protein markers (Part I only, Week 0, 12)
CL-301	Week 8, 16, 24, 32, 40, 48 Muscle strength as measured by HHD; Walking ability as measured by the 6MWT; Arm raising ability as measured by the weighted arm lift test; Muscle strength on mobility domain score by GNEM-FAS	Week 8, 16, 24, 32, 40, 48 The total score on a 45-item self-report of INQoL. Week 24, 48 The CGI Severity scale (CGI-S, baseline only), and improvement scale (CGI-I, at each subsequent visit).	Week 0, 8, 16, 24, 32, 40, 48 CK Serum SA Week 0, 16, 32, 48 Free, total and bound urine SA Urine ManNAc
CL-203	Week 0, 12, 24, 36, 48 Muscle strength by GNEM-FAS Expanded Version total score; Upper extremity strength as measured by HHD Lower extremity muscle strength as measured by HHD	Week 0, 12, 24, 36, 48 Health-related quality of life as assessed by SF-36 Symptom severity as measured by PGI-S (baseline only) and PGI-C (at each subsequent visit)	Week 0, 12, 24, 36, 48 CK Free serum SA Serum aceneuramic acid Free, total and bound Urine SA Urine ManNAc
CL-302 (Patients from 202/301)	Week 0, 8, 16, 24, 48, 72, 96 Muscle strength as measured by HD; Walking ability as measured by the 6MWT; Arm raising ability as measured by the weighted arm lift test; Change in muscle strength on mobility domain score by GNEM-FAS.	Week 0, 8, 16, 24, 48, 72, 96 The total score on a 45-item self-report of INQoL.	Week 0, 8, 16, 24, 48, 72, 96 CK Free serum SA. Urine ManNAc

Study	Functional Test	Questionnaire	Biomarker
CL-302 (Patients from CL203)	Week 0, 24, 48, 72, 96 Muscle strength in GNEM-FAS Expanded Version total score; Muscle strength as measured by HHD.	Week 0, 24, 48, 72, 96 Health-related quality of life as assessed by SF-36	Week 0, 8, 16, 24, 48, 72, 96 CK Free serum SA. Urine ManNAc

10.5 Schedule of Events

ASSESSMENTS AND EVENTS*	SCREENING/ BASELINE ^a	TREATMENT PERIOD							SAFETY FOLLOW UP (+ 5 DAYS) ^m
		MONTH 2 (WEEK 8) VISIT (± 5 DAYS) [†]	MONTH 4 (WEEK 16) VISIT (± 5 DAYS) [†]	MONTH 6 (WEEK 24) VISIT (± 5 DAYS)	MONTH 12 VISIT (WEEK 48) (± 2WEEKS)	MONTH 18 VISIT (WEEK 72) (± 2WEEKS)	MONTH 24 (WEEK 96) OR EARLY TERMINATION VISIT (± 2WEEKS) ^l		
SAFETY ASSESSMENTS (ALL SUBJECTS)									
INFORMED CONSENT	X								
MEDICAL HISTORY	X								
INTERVAL HISTORY ^b	X	X	X	X	X	X	X		
PHYSICAL EXAMINATION ^c	X	X	X	X	X	X	X		
VITAL SIGNS	X	X	X	X	X	X	X		
HEMATOLOGY, CHEMISTRY PANEL, URINALYSIS	X	X	X	X	X	X	X		
PREGNANCY TEST	X	X	X	X	X	X	X		
CONCOMITANT MEDICATIONS	X	X	X	X	X	X	X	X	
SUICIDAL IDEATION AND BEHAVIOR (C- SSRS) ^d	X	X	X	X	X	X	X		
ADVERSE EVENTS	X	X	X	X	X	X	X	X	
PHARMACODYNAMIC ASSESSMENTS (ALL SUBJECTS)									
BIOMARKERS: CK, FREE SERUM SA, AND BIOMARKERS OF SIALYTATION AND OTHER BIOMARKERS ^e	X	X	X	X	X	X	X		
FREE, TOTAL AND BOUND URINE SA LEVELS ^f	X	X	X	X	X	X	X		
URINE TEST FOR MANNAC ^g	X	X	X	X	X	X	X		

ASSESSMENTS AND EVENTS*	SCREENING/ BASELINE ^a	TREATMENT PERIOD						
		MONTH 2 (WEEK 8) VISIT (± 5 DAYS) [‡]	MONTH 4 (WEEK 16) VISIT (± 5 DAYS) [‡]	MONTH 6 (WEEK 24) VISIT (± 5 DAYS)	MONTH 12 VISIT (WEEK 48) (± 2WEEKS)	MONTH 18 VISIT (WEEK 72) (± 2WEEKS)	MONTH 24 (WEEK 96) OR EARLY TERMINATION VISIT (± 2WEEKS) ¹	SAFETY FOLLOW UP (+ 5 DAYS) ^m
TREATMENT DISPENSING AND COMPLIANCE (ALL SUBJECTS)								
TREATMENT DISPENSED ^h	X	X	X	X	X	X		
TREATMENT COMPLIANCE		X	X	X	X	X	X	
EFFICACY ASSESSMENTS (UX001-CL202 AND UX001-CL301 SUBJECTS)ⁱ								
DYNAMOMETRY	X	X	X	X	X	X	X	
6-MINUTE WALK TEST (6MWT)	X	X	X	X	X	X	X	
SIT-TO-STAND TEST	X	X	X	X	X	X	X	
WEIGHTED ARM LIFT TEST	X	X	X	X	X	X	X	
GNE MYOPATHY FUNCTIONAL ACTIVITIES SCALE (GNEM-FAS)	X	X	X	X	X	X	X	
INDIVIDUALIZED NEUROMUSCULAR QUALITY OF LIFE QUESTIONNAIRE (INQoL)	X	X	X	X	X	X	X	
EFFICACY ASSESSMENTS (UX001-CL203 SUBJECTS)								
DYNAMOMETRY ^j	X			X	X	X	X	
GNEM-FAS ^k	X			X	X	X	X	
SHORT FORM HEALTH SURVEY-36 (SF-36)	X			X	X	X	X	

Refer to study-related materials for recommended timing and order of assessments to be administered at each study visit.

[‡] Subjects who roll-over from the UX001-CL203 study will not have a Month 2 or Month 4 visit. Assessments at these visits will only be performed for subjects who roll-over from the UX001-CL202 and UX001-CL301 studies. UX001-CL202 subjects will complete the same efficacy assessments as the subjects who rollover from UX001-CL301.

- a. Potential subjects can be screened up to 5 days after the last dose on the parent study. Baseline Visit should be not be more than 5 days after Screening visit. Subjects can have a concurrent Screening and Baseline visits. Study drug will be dispensed only after all study procedures at the Baseline Visit have been performed. For subjects who discontinue prior to completing the study, every reasonable effort should be made to perform the Early Termination (ET) procedures within four weeks of discontinuation.
- b. Interval history will include any signs, symptoms, or events (i.e. falls) experienced by the subject since the prior study visit that are not related to study procedure(s) performed at prior study visits or study drug. Interval history may include exacerbation or improvement in existing medical conditions (including the clinical manifestations of GNEM) that might interfere with study participation, safety, and/or positively or negatively impact performance of functional assessments.
- c. The physical examinations at Baseline/Screening, including a neurological examination; all others will be brief physical examinations. If a patient is unable to stand or has significant postural issues that interfere with collection of a standing height, self-reported adult height should be captured.
- d. Baseline C-SSRS administered at Baseline/Screening visit (may be same as last visit in parent study). Since Last Visit C-SSRS administered at all subsequent visits.
- e. Serum will be obtained at all study visits to evaluate creatine kinase (CK), serum SA and potential biomarkers of sialylation, and other markers of muscle injury and remodeling.
- f. Blood samples, preferably pre dose, and first-morning void urine will be collected to assess trough SA levels; record volume of urine collected.
- g. An aliquot from first morning void urine will be used for assessment of ManNAc; record volume of urine collected.
- h. Subjects should be instructed to return unused study drug and packaging to every visit. Note that all subjects being treated with 12 g/day Ace-ER in UX001-CL202 will be transitioned to 6 g/day Ace-ER dose in this protocol.
- i. For UX001-CL202 subjects, assessments that cannot be safely performed by a subject due to disease progression should not be administered.
- j. For subjects enrolling from UX001-CL203, lower extremity muscle strength for knee extensors muscle group only.
- k. For subjects enrolling from UX001-CL203, the GNEM-FAS Expanded version will be used.
- l. The Early Termination Visit occurs if a subject discontinues prior to completing the study or no longer wants to participate in the study. Every reasonable effort should be made to have subjects return to the clinic within 4 weeks of discontinuation and perform the Early Termination procedures; however, subjects who are unable to return to the clinic will be given the option of having an Early Termination Visit telephone call within 4 weeks of discontinuation from study, where appropriate information will be collected by the clinical site.
- m. Safety Follow-up visit to be conducted by phone 30 days (+5 days) after last dose of study drug.

10.6 Adverse Events to Monitor

10.6.1 Gastrointestinal MedDRA Query

The following MedDRA PTs are included in the gastrointestinal SMQ version 17.1.

Narrow Scope	Broad Scope
Abdominal discomfort	Anorectal swelling
Abdominal distension	Antacid therapy
Abdominal pain	Antidiarrhoeal supportive care
Abdominal pain lower	Antiemetic supportive care
Abdominal pain upper	Breath odour
Abdominal symptom	Chest pain
Abdominal tenderness	Colonic lavage
Abnormal faeces	Dysphagia
Aerophagia	Early satiety
Anorectal discomfort	Gastritis prophylaxis
Bowel movement irregularity	Gastrointestinal disorder therapy
Change of bowel habit	Gastrointestinal tract irritation
Constipation	Gastrooesophageal reflux prophylaxis
Defaecation urgency	Glycogenic acanthosis
Diarrhoea	Hypovolaemia
Epigastric discomfort	Laxative supportive care
Eruption	Malabsorption
Faecal volume decreased	Mucous stools
Faecal volume increased	Oesophageal polymer implantation
Faeces hard	Pernicious anaemia
Faeces soft	Post procedural constipation
Flatulence	Post procedural diarrhea
Frequent bowel movements	Post-tussive vomiting
Gastrointestinal pain	Probiotic therapy
Gastrointestinal sounds abnormal	Procedural nausea
Gastrointestinal toxicity	Procedural vomiting
Infrequent bowel movements	Prophylaxis against diarrhoea
Nausea	Prophylaxis of nausea and vomiting
Non-cardiac chest pain	Regurgitation
Oesophageal discomfort	Retching
Oesophageal pain	Steatorrhoea
Premenstrual cramps	Vomiting projectile
Vomiting	

10.6.2 Liver-Related Investigations

The following MedDRA PTs are included in the category “liver-related investigations.”

Alanine aminotransferase abnormal
Alanine aminotransferase increased
Aspartate aminotransferase abnormal
Aspartate aminotransferase increased
Gamma-glutamyl transferase abnormal
Gamma-glutamyl transferase increased
Hepatic enzyme abnormal
Hepatic enzyme increased
Liver function test abnormal
Transaminases abnormal
Transaminases increased

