#### **5.2.4 Summary of Overall Risks and Potential Benefits**

GNEM is a rare and severely debilitating disease of adult onset myopathy and progressive muscle weakness with no currently approved therapy and significant unmet medical need. Strong pre-clinical evidence demonstrated that direct substrate replacement therapy may be a promising therapeutic approach for patients with GNEM. Aceneuramic acid is chemically identical to the endogenous monosaccharide sialic acid and its extended release formulation leads to stable improvement of SA levels.

Aceneuramic acid at a dose of 6 g/day has demonstrated positive pharmacodynamic effects such as increasing tissue and serum SA levels as well as lowering of serum creatine kinase

(CK) levels that support the clinical efficacy observed in a randomized, double-blind, placebo-controlled study. The clinical efficacy data at 6 g/day demonstrates muscle strength stabilization and preservation of functional independence relative to placebo or lower dose treatment. Safety information collected over approximately 2.5 years demonstrates that aceneuramic acid has a favorable safety profile.

Each clinical study assessed AEs and SAEs at every scheduled study visit from the time of informed consent. As expected with a substrate replacement therapy, Ace-ER has been well tolerated in clinical studies to date. Levels of free SA in serum during 6 g/day administration were only 2 fold greater than in healthy volunteers. There have been no treatment-related serious adverse events and only one withdrawal due to an adverse event over the 2.5 years of observation. Acceptable tolerability has also been demonstrated by a high treatment compliance rate as well by the fact that all subjects who completed the pivotal study elected to participate in the extension study. The incidence of adverse events of gastrointestinal (GI) disturbance including flatulence, dyspepsia, and diarrhoea were greater in the treatment groups than placebo during the first 24 weeks of the pivotal study. Exposure adjusted rates of these GI events were similar when comparing 6 g/day to placebo. Mildly elevated transaminases occurred but were considered most likely related to the underlying skeletal muscle disease rather than to liver injury.

Ace-ER treatment at 6 g/day clearly has a positive benefit-risk profile that supports the proposed indication of treatment of adult patients with GNEM, and has the potential to impact an unmet medical need for GNEM patients.

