**Table 7.5.5.5.1: Clinical Laboratory Assessments for Safety**

Chemistry	Hematology	Urinalysis+
Alanine aminotransferase (ALT)	Hematocrit	Appearance
Alkaline phosphatase	Hemoglobin	Color
Amylase	Mean corpuscular hemoglobin (MCH)	pH
Aspartate aminotransferase (AST)	MCH concentration (MCHC)	Specific gravity
Bilirubin (direct and total)	Mean corpuscular volume (MCV)	Ketones
Blood urea nitrogen (BUN)	Platelet count	Protein
Calcium	Red blood cell (RBC) count	Glucose
Chloride	Reticulocyte count	Bilirubin
Cholesterol (total)	Neutrophil count (absolute and %)	Nitrite
Creatine kinase 		Urobilinogen
Creatinine	Lymphocyte count (absolute and %)	Hemoglobin
Gamma-glutamyl transpeptidase (GGT)	Monocyte count (absolute and %)	Creatinine 
Glucose	Eosinophil count (absolute and %)	ManNAc 
Lactate dehydrogenase (LDH)	Basophil count (absolute and %)	Leukocyte esterase
Lipase	White blood cell (WBC) count	Pregnancy test (if applicable)
Phosphorus	WBC differential	Blood/RBC
Potassium		
Protein (albumin and total)		*Special assessment
Sodium		Serum pregnancy test if a positive urine pregnancy test
Triglycerides		

+ Microscopic examination will be performed only if dip stick is abnormal for protein, leukocyte esterase, blood or nitrite. Microscopic examination may include WBC,

RBC, Epithelial Cells, Squamous, Epithelial Cells, Transitional, Epithelial Cells, Renal Tubular, Hyaline Casts, WBC Casts, RBC Casts, Waxy Casts, Granular Casts, Calcium Oxalate Crystals, Uric Acid Crystals, Triphosphate Crystals, Yeast, Bacteria, Amorphous Urates and Amorphous Phosphates

 Also designated as PD variable (Section 7.5.2.8)

 Relevant to Drug Concentration Measurements (Section 7.5.3)

 To screen for use of prohibited medications (Section 7.4.6.1)

Subjects who experience a SAE possibly or probably related to study drug or other AE of concern may, at the discretion of the Investigator (and/or medical monitor), have additional blood samples taken for safety laboratory tests.

Upon completion of protocol-specified laboratory tests, leftover blood and urine samples from each visit may be used for additional exploratory research, eg, biomarker research. The leftover samples from this study will not be used for genetic testing.

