8.7.1.1 Adverse Events to Monitor

Adverse events to be monitored are included in Appendix [10.5](#) by MedDRA preferred terms in categories of gastrointestinal AEs and liver-related investigations.

Tables summarizing patient incidents for the monitored adverse events will be generated.

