8.7.3 Clinical Laboratory Parameters

Descriptive statistics for clinical laboratory values and changes from the CL302 baseline values at each visit will be presented. The number and percentage of abnormalities for each lab parameter at each assessment time point will be reported.

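### The SAP's monitored liver category has no bilirubin or alkaline phosphatase term, and no planned summary links a subject's ALT/AST to same-visit bilirubin, ALP, GGT or CK

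*SAP*

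**What the plan says.** SAP 8.7.1.1 singles out two groups of adverse events for monitoring, set out "by MedDRA preferred terms in categories of gastrointestinal AEs and liver-related investigations". The planned output is brief: "Tables summarizing patient incidents for the monitored adverse events will be generated". Nothing says whether the liver table will have a row for each preferred term or one pooled count.

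The liver list is in SAP 10.6.2, introduced by "The following MedDRA PTs are included in the category". It covers ALT, AST, GGT, hepatic enzyme, liver function test and transaminase terms. It includes "Gamma-glutamyl transferase increased" and the non-specific "Liver function test abnormal". There is no bilirubin term and no ALP term.

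On transaminases, protocol 5.2.4 reports from earlier studies: "Mildly elevated transaminases occurred but were considered most likely related to the underlying skeletal muscle disease rather than to liver injury".

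The chemistry panel in protocol Table 7.5.5.5.1 includes ALT, AST, ALP, direct and total bilirubin, GGT and CK. Protocol 7.5.5.5 has it drawn at every visit except the follow-up call. SAP 8.7.3 plans descriptive statistics, changes from the CL302 baseline and this: "The number and percentage of abnormalities for each lab parameter at each assessment time point will be reported". Protocol 7.6.6 likewise works measurement by measurement.

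**The concern.** Long-term safety is the primary objective, and the study is single-arm with no formal data monitoring committee (SAP 2.1, 3.3, 3.7). Without a concurrent control there is no direct estimate of how often ALT or AST rises from muscle disease alone. The main internal evidence on origin is therefore what happens to the other markers in the same subject at the same visit. Those markers are collected, but no planned summary brings them together.

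This could mislead in two ways. New or worsening muscle-derived AST elevations reported as AEs would count as liver events. Conversely, a true hepatic elevation could be put down to muscle because no table shows whether bilirubin, ALP or GGT rose with it. In addition, a subject whose only relevant AE is coded to a bilirubin or ALP term would not be counted in the group meant to gather liver findings.

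**Working it through.** The plan gives no sample-size, power or event figure on this point, so there is none to reproduce. The check is a count of the list, a comparison with the laboratory panel, and a look at what marginal tables can show.

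**1. Count of preferred terms in SAP 10.6.2**

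| Analyte named | Terms | Share of 11 |
|---|---|---|
| ALT | 2 | 18% |
| AST | 2 | 18% |
| Transaminases | 2 | 18% |
| GGT | 2 | 18% |
| Hepatic enzyme (no analyte named) | 2 | 18% |
| Liver function test (no analyte named) | 1 | 9% |
| Bilirubin | 0 | 0% |
| Alkaline phosphatase | 0 | 0% |

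Total: 2 + 2 + 2 + 2 + 2 + 1 = 11. Aminotransferase terms: (2 + 2 + 2)/11 = 6/11 = 55%. Counting only terms that name ALT or AST: 4/11 = 36%. These are shares of term names, several of them abnormal/increased pairs, and not shares of events.

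**2. Panel against list and summaries**

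| Analyte | Measured at each clinic visit | Own term in 10.6.2 | Abnormality counts under SAP 8.7.3 | Joint summary with ALT/AST |
|---|---|---|---|---|
| GGT | Yes | Yes | Yes | None |
| Bilirubin | Yes | No | Yes | None |
| ALP | Yes | No | Yes | None |
| CK | Yes | No (muscle marker) | Yes | None |

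Neither document states a threshold in multiples of ULN.

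**3. What marginal tables leave open**

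If *a* of *N* subjects have raised ALT and *b* have raised bilirubin at a visit, separate tables fix the overlap only to the range from max(0, *a* + *b* − *N*) to min(*a*, *b*). For illustration only, take *a* = *b* = 5 and *N* = 165 (the protocol's planned enrolment). The lower bound is max(0, 5 + 5 − 165) = 0 and the upper bound is 5. The same tables fit ten different subjects with one abnormality each, or five subjects with both. With the SAP's figure of 180 subjects the bounds are unchanged. The same holds for ALT/AST against ALP, GGT or CK.

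**4. Where a bilirubin or ALP event would appear**

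- As an AE: clinically significant laboratory changes are recorded as AEs where appropriate (protocol 7.5.5.9), and all treatment-emergent AEs are tabulated by SOC and preferred term (SAP 8.7.1).
- As a laboratory value: in the abnormality counts (SAP 8.7.3) and the data listings (SAP 8.1).
- In the monitored liver table: only if it is coded to a non-specific term such as the liver function test or hepatic enzyme terms.

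**The case against.** The strongest reply is that nothing is missing from the safety analysis. Bilirubin and ALP events have their own rows in the general AE tables, every laboratory parameter gets abnormality counts, and the listings let a reader line up same-visit values for any subject. Protocol 7.3.3.1 also provides for periodic aggregate review of laboratory abnormalities. This stands, and it defeats a stronger reading that a reader might take from the list, namely that the plan cannot capture a bilirubin event. It can; the event only falls outside one supplementary grouping.

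A second reply is that the list is not blind to origin. It has two GGT terms, and the muscle attribution in protocol 5.2.4 concerns transaminases, not GGT. If the table is shown by preferred term, some separation is possible. This also stands, but the SAP does not commit to that display, and a pooled count would not separate anything.

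Third, stable muscle-derived elevations would mostly not enter the count. AEs are new or worsening conditions (protocol 8.5.4.1), and events continuing from the parent study are excluded unless severity worsens (SAP 8.7.1). This narrows the dilution to new or worsening elevations.

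Fourth, the category feeds descriptive tables with no test or decision rule, does not alter the primary endpoint, and SAP 8.1 already allows additional tables. All true, and this limits the consequence. But linking values by hand from listings, or adding a table after the data are seen, is weaker than a summary whose thresholds were fixed beforehand.

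**Conclusion.** The point holds as a limited gap in planned reporting. The monitored liver category has 0 of 11 terms for bilirubin or ALP, 6 of 11 are aminotransferase terms, and no planned summary joins a subject's ALT/AST to the four other markers drawn at the same visit. Liver versus muscle origin must therefore be inferred from separate marginal tables, which cannot show co-occurrence.

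The size of any misclassification cannot be stated, because the documents give no rate of ALT or AST elevation. A reader might infer from protocol 7.5.2.8, where CK is at least twice ULN in approximately 50% of patients, that about half of subjects have a muscle source of raised ALT/AST. The documents do not support that step: they do not relate CK level to ALT or AST, and protocol 7.5.6 describes CK in these patients as mildly elevated or normal. The CK figure is context only. Likewise, the 55% describes the make-up of the list and not the share of events that come from muscle, and protocol 5.2.4 speaks only of mild elevations and of a most likely cause.

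The conclusion assumes that the list is applied as written. How far pooling hides origin depends on a display that the SAP leaves unstated.

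**What to change.** - **SAP 10.6.2:** add the bilirubin and alkaline phosphatase preferred terms.
- **SAP 8.7.1.1:** state that the monitored-event table is shown by preferred term, with the ALT, AST and transaminase terms on a line separate from the rest. Correct the cross-reference at the same time: this section points to Appendix 10.5, which is the Schedule of Events, while the list is in Appendix 10.6.
- **SAP 8.7.3:** add one per-subject cross-tabulation and an accompanying listing, by parent study and overall, of ALT or AST elevation against same-visit total bilirubin, ALP, GGT and CK. The sponsor should prespecify the ULN multiples, since the documents give none.

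The cost is a few added terms, one table and one listing, all from samples already drawn. The monitored-event count may rise slightly because bilirubin and ALP events would now be included.
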